9.4. Pregnancies

Pregnancy data will not be collected in this study.

9.5. Clinical Laboratory Evaluations

Listing 9 presents results of all clinical laboratory testing of dried blood spot and whole blood samples. Investigations into the concordance between positive dried blood spot and confirmatory whole blood samples are described in Section 13.

9.6. Vital Signs and Physical Evaluations

No vital signs or physical exams will be conducted for this study.

10. PHARMACOKINETICS

No pharmacokinetic analyses will be conducted.

11. IMMUNOGENICITY

No immunogenicity analyses will be conducted.

12. PARTICIPANT AND PROVIDER SATISFACTION EVALUATION

12.1. Participant and Provider Satisfaction Responses

Summaries of responses to questionnaires from participant and provider satisfaction questionnaires will be presented by time point of questionnaire: after training, one month post discharge, and after study completion. Questionnaire responses will be converted to numeric values as described in Section 3.3.13. The responses to questions asked on the Likert Scale will be converted to numbers from 1-5 and the number of non-missing responses, as well as the mean, standard deviation, median, minimum and maximum responses will be summarized. For Yes/No questions, the number of non-missing responses as well as the number and proportion of "Yes" responses will be summarized. For questions asking for the best reason, out of those who answered "Yes" to the preceding question, the number and proportion of participants who picked each option will be summarized.

For summaries of the participant and provider satisfaction data, data will be presented in the DBS group from the ITT population for each time point of interest.

The tables will present data from the participants in the DBS group corresponding to each questionnaire time point (Table 31, Table 33, and Table 34). All provider satisfaction responses will be summarized in Table 35.

Individual participant and provider satisfaction responses are listed in Listing 15, Listing 16, Listing 17, and Listing 18.

12.2. Participant and Provider Satisfaction Composite Scores

Composite scores for overall participant satisfaction with email and mobile technology and overall satisfaction with kit contents and testing and shipping procedures will be presented for the one month postdischarge and after study completions surveys (Table 32). Composite scores for overall provider satisfaction with CMV DBS self-collection results will be presented for the after-study completion survey (Table 35).

For each survey timepoint, the composite scores will be defined as the mean of Likert scale responses converted to the numeric scale to the questions defined below.

	Composite Score	Component Survey Questions						
Participant		The self-collection teaching videos are helpful and easy to follow.						
	Overall satisfaction with	The web and mobile phone site is easy to use and provides me with the information I need to do the testing at home.						
	email and mobile technology	The web or mobile phone options give me the choices I want for how and when I received the reminders.						
		The email or mobile phone messages remind me to do the self-collection.						
	Overall satisfaction with	The self-collection kit had everything I needed to do the testing.						
	kit content, and testing and shipping procedures	The CMV dried blood spot self-collection is easy.						
	simpping procedures	Scheduling USPS to pick up my sample is easy.						

	Composite Score	Component Survey Questions
Provider	Overall satisfaction with CMV dried blood spot self-	DBS testing will increase adherence to CMV surveillance late after HCT.
	collection results	The results of the finger stick CMV self-collection were available to me in an easy and timely fashion.
		I was confident with the results of the CMV dried blood spot self-collection results
		If I have the results of the CMV self-collection, I do not feel I need an additional plasma blood draw to decide on treatment for my patient
		I would participate in another study with use of this type of blood self-collection

13. MOBILE TECHNOLOGY, DEVICE AND SHIPMENT EVALUATION

Mobile technology, device and shipment evaluation will include summaries of time from scheduled pick-up at participant residence to arrival at lab, the number of samples unevaluable due to lack of amplification or inhibition, and number of mobile technology failures.

The number of DBS testing reminder failures will be summarized (Table 39). The number of failed reminders overall, number of participants who had failed reminders, and the number of failed reminders per participant will be presented. In addition, the number of participants who missed a recommended DBS test following a failed reminder and the number of tests missed following failed reminders will be summarized. A listing presenting the DBS testing reminder configuration data is presented in Listing 10.

The number of samples with collection time, shipment time and arrival time entered, as well as the mean, standard deviation, minimum, maximum and median hours from scheduled pick-up to arrival at study laboratory will be summarized by transplant site and participants' perceived ease of access to blood draw facility for the participants in DBS arm (Table 36).

The number and proportion of unevaluable samples, and the number and proportion of participants with unevaluable samples, will be summarized by transplant site. (Table 37).

The Lin's concordance correlation coefficient will be calculated (Table 38). Sensitivity, specificity and predictive values of CMV detection in confirmatory DBS versus confirmatory WB testing will be reported. In addition, a correlation between the confirmatory DBS result and the confirmatory WB result will be visualized in Figure 5. A Bland-Altman plot of difference between the confirmatory DBS result and the confirmatory WB result will be presented in Figure 6.

For sample collection and sample delivery failures, the total number of failures, the number of participants with failures and the median, minimum and maximum number of failures per participant will be summarized by sample type, i.e. DBS, WB or any sample, in Table 40.

14. LOCAL PROVIDER CARE EVALUATION

The number of participants in each intervention group receiving pre-emptive therapy for CMV disease, as well as the mean and standard deviation of viral load at time of the decision to initiate pre-emptive therapy, by transplant site and participants' perceived ease of access to blood draw facility, as well as overall, will be summarized (Table 41).

At each quarterly contact, the least-frequent clinician-recommended monitoring interval recorded for each participant up until 90 days post-HCT (first contact), 180 days post-HCT (second contact), 270 days post-HCT (third contact) and 365 days post-HCT (final contact) will be categorized as described in Section 3.3.7.

The number and proportion of participants in each of the groups between enrollment and the first, second, third and final contacts will be summarized by intervention group, as well as by stratification variables and overall (Table 42, Table 43, Table 44, and Table 45). Note that University of Minnesota results will be excluded from the perceived ease of access stratification as this site recorded actual number of clinician-recommended CMV monitoring tests completed instead of the clinician-recommended CMV monitoring intervals.

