3.2.3. Exploratory Outcome Measures

- 1. Mean time from scheduled pick-up at participant residence (DBS tests) or blood draw facility (plasma sample) to arrival at the laboratory (hours) at all applicable test points throughout the study period
- 2. Number of mobile technology failures, sample collection failures, sample delivery failures, and sample viability failures.
- 3. Sensitivity, specificity and predictive values of CMV detection in DBS versus plasma testing
- 4. Number and type of key transplant characteristics in randomized participants and observational participants
- 5. Describe the baseline participant demographics of randomized cohort and observational cohort.
- 6. Number of participants with end-organ CMV disease (possible and proven/possible) at 1 year after HCT in randomized participants and observational participants
- 7. Describe local provider CMV treatment viral load treatment thresholds
- 8. Describe local provider CMV monitoring interval recommendations
- 9. Report composite scores of different variables of participant and provider satisfactions according to the 5-point Likert scale questionnaires.

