3.3.14. Unanticipated Adverse Device Effects or Device Failures

False positive results and false negative results from the testing conducted at the University of Washington Laboratory on DBS samples are Unanticipated Adverse Device Effects (UADEs) and are considered Device Failures and will be reported as an Unanticipated Problem.

The following rules will be used to identify possible false positive or false negative results:

False Positive is reported in either of the following cases:

- A DBS sample is positive at a viral load above the treatment threshold at the respective site and a confirmatory WB sample is negative and collected within 3 days of the DBS sample.
- A confirmatory DBS is positive at a viral load above the treatment threshold at the respective site and a confirmatory WB sample is negative and collected on the same day.

False Negative is reported in either of the following cases:

- A CMV PCR result identified in the quarterly chart review is positive at a viral load above the treatment threshold at the respective site and a DBS sample is negative and collected within 3 days of the clinical plasma sample.
- A confirmatory DBS sample is negative and a confirmatory WB sample is positive at a viral load above the treatment threshold at the respective site collected on the same day.

Both DBS and WB results for UADE monitoring are obtained from the laboratory data uploaded by the University of Washington Laboratory (See Section 3.3.8 and Section 3.3.9 for further details).

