- CMV prophylaxis for at least 30 days from the day of transplant to 100 days post-transplant
- Participant baseline demographics will be presented for the randomized and observational cohorts. Stratification variables will be presented for the randomized cohort as these were not collected in the observational cohort.
- The number of participants in the randomized and observational cohorts with possible, probable or proven end-organ CMV disease by 1 year after HCT will be reported. These data were collected on the CMV Infection or Disease eCRF at each follow-up.
- The local provider CMV viral load treatment threshold will be reported. These data were entered on the CMV Viral Treatment Threshold eCRF at enrollment or when new thresholds became effective.
- The local provider CMV clinician recommended CMV monitoring intervals will be reported as described (Section 3.3.4, 3.3.5, and 3.3.7).

• The composite scores of different variables of participant and provider satisfactions according to the 5-point Likert scale questionnaires will be reported as described. (Section 3.3.12, 12.2).

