14.6 Local Provider Care Data

Table 41:Primary Care Physician Viral Load Treatment Thresholds, by Intervention Group,
Transplant Site and Perceived Ease of Access to Blood Draw Facility

		BS =X)		OC =X)	All Randomized (N=X)		
Variable Category	Num. Treated Part.	Treatment Threshold (IU/mL)	Num. Treated Part.	Treatment Threshold (IU/mL)	Num. Treated Part.	Treatment Threshold (IU/mL)	
	n	Mean (SD)	n	Mean (SD)	n	Mean (SD)	
Transplant Site							
Fred Hutchinson Cancer Research Center	XXX	xx.x (xx.x)	XXX	xx.x (xx.x)	XXX	xx.x (xx.x)	
Memorial Sloan Kettering Cancer Center	XXX	xx.x (xx.x)	XXX	xx.x (xx.x)	XXX	xx.x (xx.x)	
University of Minnesota	XXX	xx.x (xx.x)	XXX	xx.x (xx.x)	XXX	xx.x (xx.x)	
MD Anderson Cancer Center	XXX	xx.x (xx.x)	XXX	xx.x (xx.x)	XXX	xx.x (xx.x)	
Perceived Ease of Access to Blood Draw Facility							
Easy	XXX	xx.x (xx.x)	XXX	xx.x (xx.x)	XXX	xx.x (xx.x)	
Difficult	XXX	xx.x (xx.x)	XXX	xx.x (xx.x)	XXX	xx.x (xx.x)	
Overall	XXX	xx.x (xx.x)	XXX	xx.x (xx.x)	XXX	xx.x (xx.x)	
N=Number of participants in the Safety Population							

Table 42:Least-Frequent Clinician-Recommended Monitoring Interval Categories by 90 Days Post-HCT, by Intervention Group and
Stratification Variables

[Implementation note: Within each variable and category, the percentages should be row percentages within each intervention group.]

					Transpl	lant Site	Pe			s to Blood sity of Min		lity			
	Least-Frequent Clinician- Recommended Monitoring	Cancer	itchinson Research nter	Ketterin	ial Sloan g Cancer nter		rsity of esota ^a		nderson [.] Center	Ea	ısy	Diff	ïcult	Ove	erall
Treatment Arm	Interval	n	%	n	%	n	%	n	%	n	%	n	%	n	%
DBS $(N = X)$	No Further Monitoring Required	XXX	xx.x	xxx	xx.x	xxx	xx.x	xxx	xx.x	xxx	xx.x	xxx	xx.x	xxx	xx.x
	Weekly	XXX	XX.X	xxx	XX.X	xxx	XX.X	xxx	XX.X	xxx	XX.X	xxx	XX.X	XXX	XX.X
	Bi-Weekly	xxx	xx.x	xxx	xx.x	xxx	xx.x	xxx	xx.x	xxx	xx.x	xxx	xx.x	XXX	xx.x
	Monthly	xxx	xx.x	xxx	XX.X	xxx	xx.x	xxx	XX.X	xxx	XX.X	xxx	xx.x	XXX	xx.x
	Quarterly	XXX	xx.x	xxx	XX.X	xxx	xx.x	xxx	XX.X	xxx	XX.X	xxx	XX.X	XXX	XX.X
SOC (N = X)	No Further Monitoring Required	XXX	xx.x	XXX	XX.X	XXX	XX.X	XXX	XX.X	XXX	XX.X	XXX	XX.X	xxx	XX.X
	Weekly	XXX	XX.X	xxx	XX.X	xxx	xx.x	xxx	XX.X	xxx	XX.X	xxx	XX.X	XXX	XX.X
	Bi-Weekly	XXX	XX.X	xxx	XX.X	xxx	XX.X	xxx	XX.X	xxx	XX.X	xxx	XX.X	xxx	XX.X
	Monthly	XXX	XX.X	xxx	XX.X	xxx	XX.X	xxx	XX.X	xxx	XX.X	xxx	XX.X	xxx	XX.X
	Quarterly	XXX	XX.X	xxx	XX.X	xxx	xx.x	xxx	XX.X	xxx	XX.X	xxx	XX.X	XXX	XX.X

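### SAP Section 14 fills the column that Table 41 labels as treatment threshold with viral load at the start of therapy, and no listed display reports the thresholds collected on their own eCRF

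*SAP*

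**What the plan says.** Exploratory outcome 7 (SAP 3.2.3, repeated from Protocol 3.2.3) is "Describe local provider CMV treatment viral load treatment thresholds". SAP 4.5.3 expands it: "The local provider CMV viral load treatment threshold will be reported". It then gives the source: "These data were entered on the CMV Viral Treatment Threshold eCRF at enrollment or when new thresholds became effective". It cites no table number.

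SAP Section 14 is the text that defines Table 41. It specifies a count of participants receiving pre-emptive therapy in each arm, "as well as the mean and standard deviation of viral load at time of the decision to initiate pre-emptive therapy", by transplant site, by perceived ease of access to a blood draw facility, and overall.

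The shell of Table 41 is titled "Primary Care Physician Viral Load Treatment Thresholds, by Intervention Group", with site and ease of access as further splits. For each arm it pairs a column headed "Num. Treated Part" with a mean (SD) column headed as the treatment threshold in IU/mL.

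Elsewhere the SAP keeps the two quantities apart. Section 3.3.14 defines false results by reference to a sample "positive at a viral load above the treatment threshold at the respective site", so the threshold there belongs to the site. Listing 8 has a separate participant-level column for viral load at initiation of pre-emptive therapy.

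**The concern.** A treatment threshold is a rule that a provider or site holds before any result arrives. Viral load at initiation is what one patient's result happened to be when treatment was decided. The second depends on the first, but also on how fast the virus was rising, how long it was since the last test, and whether the provider followed the rule. It exists only for patients who were treated.

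Two things are at stake. First, outcome 7 would go unreported although the data were collected, because the only table carrying the threshold label would hold another variable. Second, Table 41 is split by arm. Test frequency and adherence are what the trial sets out to change, so viral load at initiation could differ by arm while every threshold is identical. Under the present heading, a reader would take that as a difference in provider policy.

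**Working it through.** The plan states no figure for Table 41, so there is none to reproduce. The check compares the sections and then looks at direction.

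**1. What each place says the column holds**

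| Place | Quantity | Who contributes |
|---|---|---|
| SAP 3.2.3, outcome 7 | local treatment threshold | local providers |
| SAP 4.5.3 | threshold, from the CMV Viral Treatment Threshold eCRF | not limited to treated participants |
| SAP Section 14 | viral load at the decision to start therapy | treated participants |
| Table 41 shell, title and heading | threshold | shown beside the number treated |
| Listing 8 | viral load at initiation | participants on pre-emptive therapy |

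Section 14 disagrees with 4.5.3 and with the shell's own title and heading.

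**2. Whether another display covers the gap.** The lists of Tables 1 to 45, Figures 1 to 6 and Listings 1 to 18 contain no other entry for the eCRF thresholds. Listing 8 covers viral load at initiation, and Listing 13 covers monitoring intervals.

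**3. Direction.** Let T be the threshold and V the viral load at initiation. If every start has V ≥ T, then mean(V) ≥ T, with equality only if every start falls exactly on T. The condition is needed: if some starts have V < T, the inequality can fail.

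**4. Illustration of the mechanism, not an estimate.** Assume exponential growth with doubling time D, a crossing of T at a uniformly distributed time within a test interval of d days, and treatment at the first test at or above T. Then

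mean(V) = T × (2^(d/D) − 1) / ((d/D) × ln 2).

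The documents give no doubling time, so D = 5, 7 and 14 days is an assumed range. T = 1,000 IU/mL is one of the two levels that Protocol 2.1.5.2 names; at 500 IU/mL every value halves.

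| Test interval d | D = 5 | D = 7 | D = 14 |
|---|---|---|---|
| 7 days | 1,689 | 1,443 | 1,195 |
| 14 days | 3,073 | 2,164 | 1,443 |
| 30 days | 15,148 | 6,229 | 2,300 |

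For d = D = 7: 1,000 × (2 − 1)/(1 × 0.693) = 1,443.

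The threshold is 1,000 in every cell, yet the mean moves with the test interval. The DBS arm adds weekly self-collection (SAP 4.4.1), while the clinician's schedule may lengthen to bi-weekly, monthly or quarterly (SAP 3.3.4). A difference between arms is therefore possible without any difference in threshold. Its direction in this trial cannot be deduced.

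**5. How early starts would offset it.** Suppose a fraction f of starts occurs at 300 IU/mL (assumed) and the rest follow the weekly model with mean r. The overall mean returns to 1,000 when f = (r − 1,000)/(r − 300).
- D = 7: 443/1,143 = 39%.
- D = 14: 195/895 = 22%.

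**The case against.** The strongest reply is that this is a contradiction between sections and not a settled analysis. A programmer working from SAP 4.5.3 and the Table 41 heading would use the threshold eCRF, and no distortion would arise. That stands, and it is why the point is put as a conflict to be resolved. It does not remove the need to act, because Section 14 is the only text that defines the table's content, and it names the other variable.

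Other points against also stand:
- The upward direction is conditional. Protocol 4.1 leaves the treatment decision to the primary care provider, on plasma viral load, and ties it to no threshold.
- Viral load at initiation is relevant to exploratory objective 6, on local treatment algorithms. Only outcome 7 requires the threshold itself.
- Viral load at initiation is not lost. Listing 8 gives it under its correct name, sorted by intervention group.
- The false-positive and false-negative rules in SAP 3.3.14 use the site threshold directly, so they are unaffected.

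A reader might go further and infer from Protocol Table 2 that the threshold would be overstated about 2.5-fold. Taking the lowest values compatible with that table, the samples at or above 500 IU/mL have a mean of at least (43 × 510 + 36,000 + 4 × 500)/48 = 1,249, and 1,249/500 = 2.5. Those at or above 1,000 have a mean of at least (21 × 1,000 + 36,000)/22 = 2,591, or 2.6 times. The documents do not support this use. The ranges printed there belong to the 44 and 21 DBS-positive samples, not to all 48 and 22. They come from residual clinical samples (145 from 69 persons) that nothing says were taken at a treatment decision. Both ratios also depend on the single value of 36,000: without it the same construction gives (43 × 510 + 4 × 500)/47 = 509, or 1.02 times, and 1.0 times.

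**Conclusion.** The mismatch holds. Section 14 specifies viral load at initiation in treated participants; the Table 41 heading and SAP 4.5.3 call for the threshold; and no other listed display supplies it. If Section 14 is followed, outcome 7 is answered with the wrong variable, and providers whose patients were never treated contribute nothing.

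If providers start at or above their threshold, the value shown overstates it by an amount that cannot be sized from the documents. The illustrative figures rest wholly on assumed doubling times. The value could also differ by arm because of detection timing alone. A reader might infer that the plan fixes an upward-biased estimate or will produce a false arm difference. Neither follows, because the sections conflict, and both effects depend on provider behaviour and detection timing that the documents do not give.

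The reach is small: one descriptive exploratory table with no hypothesis test. No primary or secondary result, sample size or error rate changes. It is still worth correcting before the tables are produced, since the remedy uses data already collected.

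**What to change.** Reconcile SAP 4.5.3, Section 14 and the Table 41 shell as follows.

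- Fill the treatment-threshold column from the CMV Viral Treatment Threshold eCRF, summarised by site and not restricted to treated participants. State the level at which the form was completed (participant, provider or site), because 4.5.3 does not say and 3.3.14 treats the threshold as a site attribute. Summarise at that level.
- Report viral load at initiation of pre-emptive therapy by arm, in treated participants, in a separate column under its own name. Add median and range, because viral loads in IU/mL are skewed.
- Cite Table 41 in 4.5.3 so that outcome 7 has a named display.

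The cost is a change of wording and one added column. Both variables are already captured, so no new data are needed.

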15. REPORTING CONVENTIONS

P-values ≥ 0.001 and ≤ 0.999 will be reported to 3 decimal places; p-values less than 0.001 will be reported as "<0.001" The mean, standard deviation, and other statistics will be reported to one decimal place greater than the original data. The minimum and maximum will use the same number of decimal places as the original data. Proportions will be presented as two decimal places; values greater than zero but <0.01 will be presented as "<0.01". Percentages will be reported to the nearest whole number; values greater than zero but < 1% will be presented as "<1"; values greater than 99% but less than 100% will be reported as >99%. Estimated parameters, not on the same scale as raw observations (e.g. regression coefficients) will be reported to 3 significant figures.

16. TECHNICAL DETAILS

SAS version 9.4 or above will be used to generate all tables and listings. Figures will be generated in either R 3.2.5 or SAS version 9.4.

17. SUMMARY OF CHANGES IN THE CONDUCT OF THE STUDY OR PLANNED ANALYSES

A sensitivity analysis excluding University of Minnesota participants for whom the site entered the actual number of monitoring tests instead of clinician-recommended tests was requested by the study team. The analysis is added in this SAP.

19. LISTING OF TABLES, FIGURES, AND LISTINGS

Table, figure, and listing shells are presented in Appendices 1, 2, and 3.

APPENDICES

